3.3 Sample Size Justification

3.3.1 Phase Ib

3 to 24 patients will be included.

3.3.2 Phase IIa

The design chosen for the calculation of the sample size is the one-stage Fleming design [2]. The hypotheses are α =0.05 one sided, power of 0.80. The one-sided null hypothesis is specified as H0: p =0.05 and the alternative H1: p= 0.20, p is the probability to achieve a CR. The sample size needed is 27 patients and the trial will be considered as positive if at least 4 CR are observed. The trial will be considered as negative if 3 CR or fewer are observed.

As the 3 to 6 patients treated during the phase Ib with the phase IIa recommended dose will be included in the efficacy analysis set of the phase IIa part, this means that 21 to 24 new patients will be enrolled in the phase IIa. This also means than the total number of patients will never exceed 45 (24+21).

4. General Analysis Definitions

4.1 General comments

Data will be analyzed using SAS (Version 9.3 or higher). Graphs will be produced in SAS or R.

No tests of significance will be carried out to compare treatment arms on baseline data. Descriptive statistics will be tabulated as follows:

- Categorical data will be summarized in contingency tables presenting frequencies and percentages. By default, those percentages will be calculated on the number of patients in the analysis population.
- Continuous data will be summarized using number of non-missing values (n), mean, standard deviation, median, first and third quartiles, minimum and maximum values.

For phase Ib results, all tables will be presented by dose level and overall. For Phase II, there will be only 1 column. Listings with individual values will be provided for all data presented in the tables.

The patients treated during the phase Ib with the phase IIa recommended dose will be analyzed in all the outputs of both phases of the trial.

4.2 Definition of Populations

4.2.1 Intent-to-treat (ITT) / safety population

The safety population will be equivalent to the ITT population and will include all patients who have received at least one dose of monalizumab. All patients will be analyzed according to the first dose of monalizumab they received.

4.2.2 Main endpoint population

The main endpoint population will include all patients:

Page 14 of 26

TPL N°: eTPL SA-02-01 Of SOP SA-02.08 TPL Effective Date: 31 Mar 2016 TPL Version: 02

Approved in Vault: 3/8/2019

- who have received at least one dose of monalizumab.
- who have received their first dose (W0D1) at least 52 weeks before the data cutoff date.

Patients who discontinued from monalizumab treatment due to disease progression before the end of 8 weeks of treatment will not be part of this population.

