# 10.5 SELECTION OF SUBJECTS

Evaluable patients: all patients who received at least 1 administration of IPH2201 will be evaluable for efficacy and safety. Patients who do not receive at least 1 administration of IPH2201 will be documented in the study report. These patients will be replaced to reach a total of 27 evaluable patients. In addition, in the two phases of the trial (Ib and IIa), patients will be replaced in case of treatment discontinuation of IPH2201 due to disease progression before the end of 8 weeks of treatment.

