 - Bone marrow aspirate: the quality of this sampling, the normocellular status for age, the cellularity status and the percentage of nucleated cells for lymphocytes will be summarized
 - Bone marrow biopsy: the quality of this sampling, the normocellular status for age, the cellularity status, the percentage of nucleated cells for lymphocytes (by the categories specified in the CRF), the presence of nodules and the main composition of these nodules will be summarized
- Medical history will be tabulated by system organ class and preferred term with four separate tables for 'ongoing' and 'not ongoing' and for related and not related to CLL.
- ECOG performance status
- Baseline laboratory serology results: HIV, HCV, Hbs antigen and Hbs antibody
- Child-bearing potential (yes or no, and reason for non-child-bearing potential), contraception practice and pregnancy test result.

7. Prior and Concomitant Treatment and procedures

The number and percentage of participants receiving a prior or concomitant medication will be displayed by ATC level 4 and first Anatomical Therapeutic Chemical class (ATC 1) for the ITT/safety population. Prior medications are the medications that

Page 17 of 26

TPL N°: eTPL SA-02-01 Of SOP SA-02.08 TPL Effective Date: 31 Mar 2016

Version: 2.0

started and stopped before the date of first administration of the study drug. The concomitant medications will be grouped in two categories. The first group of concomitant medications corresponds to the medications which started before the date of first administration of study drug and which stopped on or after this date. The second group of concomitant medications corresponds to the medications which started on or after the date of first administration of study treatment and which stopped on or after this date. The medications with missing start and end dates will be classified in this last category. The prior medications and the two groups of concomitant medications will be displayed in three separate tables.

Concomitant procedures and surgeries will also be tabulated by system organ class and preferred term for the ITT/safety population.

8. Efficacy Evaluation

All the efficacy analyses are performed on both phases of the trial. The rates of remission (\S 8.1-8.4) will be assessed using the main endpoint population. The survival endpoints (\S 8.5) will be assessed in the ITT/safety population.

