8.1 Rate of complete remission

In both phases, the rate of complete remission is assessed 52 weeks after the initiation of combined treatment

The rate of complete remission (CR) will be calculated in the main endpoint population (see §4.2.2). Within this population, the CR rate will be computed as the number of patients with a confirmed complete remission at W52 divided by the total number of patients in the main endpoint population.

The rate of complete remission with 95% confidence interval will be summarized overall and in the subgroup treated at the RP2D.

In order to claim a CR, the CR must be confirmed. In order to have a confirmed CR (cCR), the CR must be confirmed by a scan and a bone marrow assessment assessed at least 2 months after the first occurrence of CR.

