8.2 Rate of overall and partial remission

The rate of overall and partial remission is assessed 52 weeks after the initiation of combined treatment and during the in-study follow-up.

The rates of overall (i.e cCR, uCR or PR) and partial remission (PR) will be calculated in the main endpoint population (see §4.2.2). Within this population, the overall/partial remission rates will be computed as the number of patients with a any/partial remission at W52 divided by the total number of patients in the main endpoint population.

The rate of overall (and partial) remission will be summarized overall and by dose level and the 95% confidence interval for this rate will be calculated only overall and in the subgroup treated at the RP2D.

The Best Overall Response (BOR) of each patient will be displayed in a summary table. The BOR is the best response (i.e cCR, uCR, PR, SD, PD or NE) taking into account all assessment results until the last disease assessment. The PR does not need to be confirmed and there is no minimum duration for SD. However, a listing with all the derived BOR will be sent to the Sponsor for medical review before the database lock.

Page 18 of 26

TPL N°: eTPL SA-02-01 Of SOP SA-02.08 TPL Effective Date: 31 Mar 2016 TPL Version: 02
Approved in Vault: 3/8/2019

The evolution of tumor response over time will be displayed, separately by patient, via a Swimmer plot (an example of swimmer plot can be found on page 2 of the following document:

Version: 2.0

https://www.pharmasug.org/proceedings/2014/DG/PharmaSUG-2014-DG07.pdf).

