8.4 Remission with undetectable MRD

Undetectable MRD is defined as the percentage of CLL cells of all lymphocytes below 0.01%. The rate of patients in cCR at W52 with undetectable MRD in peripheral blood and bone marrow will be summarized overall and by dose level, and the 95% confidence interval for this rate will be calculated only overall for the patients in the phase Ib and for the patients in the phase IIa. Remission with undetectable MRD needs to be confirmed, i.e. CR and undetectable MRD should be met jointly and confirmed jointly. The rate of remission with undetectable MRD in peripheral blood and in bone marrow will be displayed separately.

8.5 Duration of Remission (DOR), Duration of Complete Remission (DOCR), Progression free Survival (PFS) and Overall Survival (OS)

The duration of Remission (DOR) and duration of complete Remission (DOCR) will be assessed in the main endpoint population, whereas the Progression Free Survival (PFS) and Overall Survival (OS) will be assessed in the ITT/safety population.

The DOR, for the remission assessed at 52 weeks, is defined as the time from the date of first evaluation of the remission (CR or PR) to the first documentation of progressive disease, relapsed disease or death. In case an assessment of a progressive disease, relapsed disease or death record does not exist, the duration of remission is censored at the time of the last disease assessment date. The duration of remission is only calculated for the patients with a cCR, an uCR or a PR assessed at 52 weeks.

The DOCR is calculated similarly for the patients with a cCR assessed at 52 weeks.

The PFS is defined as the time from first dose administration until the occurrence of progressive disease, relapsed disease or death from any cause. Patients without an event at the time of the analysis will be censored at his or her last disease assessment date; patient with no post-baseline assessments will be censored at the day of first dose administration.

The OS is defined as the time from first dose administration until death from any cause. Alive Patients are censored at the most recent date they are known to be alive. Subjects with no assessment post-baseline will be censored at the day of first dose administration.

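### SAP 4.2.2 drops early progressors from the response-rate denominators, although the protocol calls every dosed patient evaluable for efficacy

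*SAP*

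**What the plan says.** **SAP.** Section 4.2.2 builds the main endpoint population from patients with at least one dose of monalizumab and a first dose at least 52 weeks before the data cutoff. It then removes one group: "Patients who discontinued from monalizumab treatment due to disease progression before the end of 8 weeks of treatment will not be part of this population". The opening of SAP section 8 says the remission rates of 8.1 to 8.4 "will be assessed using the main endpoint population". Three places show what this governs:

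- 8.1, the primary rate: patients with a "confirmed complete remission at W52 divided by the total number of patients in the main endpoint population".
- 8.2, with the same denominator: "The rate of overall (and partial) remission will be summarized overall and by dose level".
- 8.4: "The rate of patients in cCR at W52 with undetectable MRD in peripheral blood and bone marrow". The denominator is not restated here; it follows from the opening of section 8.

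PFS and OS (8.5) are analysed in the ITT/safety population, which keeps these patients.

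**Success rule.** SAP 3.3.2 sets 27 patients, and "the trial will be considered as positive if at least 4 CR are observed".

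**Protocol.** Section 10.1 puts all analyses on all treated patients. Section 10.5 says that "all patients who received at least 1 administration of IPH2201 will be evaluable for efficacy and safety". It also says that, in both phases, "patients will be replaced in case of treatment discontinuation of IPH2201 due to disease progression before the end of 8 weeks of treatment". Section 4.3.2 repeats the replacement policy. Neither section says whether a replaced patient who was dosed leaves the efficacy denominator.

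**The concern.** Whether a patient belongs to the denominator depends on how that patient did. Under protocol 3.5.1 a patient who progresses stops treatment and is withdrawn, so someone who stops monalizumab for progression before 8 weeks cannot be a confirmed CR, or in remission, at week 52. Removing that patient takes one failure out of the denominator and nothing out of the numerator.

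The exclusion is also selective. A patient who stops before week 8 for toxicity or by withdrawing consent stays in. Membership therefore turns on the recorded reason for stopping, in an open-label trial.

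At stake is what the primary phase IIa rate means. As soon as there is one early progressor, the rate no longer estimates the CR probability among treated patients, and it errs in the favourable direction. The overall and PR rates by dose level rest on 3 to 6 patients, so one exclusion is far more visible there. No all-treated response rate is planned beside the reduced one.

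**Working it through.** **1. The plan's own design (SAP 3.3.2).** The inputs are one-sided alpha 0.05, power 0.80, null CR rate 0.05, alternative 0.20, N = 27 and success at 4 or more CRs. With X binomial:

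- P(X ≥ 4 | 27, 0.05) = 0.0437
- P(X ≥ 4 | 27, 0.20) = 0.818

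At N = 26 the power is 0.793. So 27 with a cutoff of 4 is reproduced and sound; the question is which patients make up the denominator.

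**2. Effect of the exclusion on the reported CR rate.** The formula is rate = CRs / denominator. The intervals are exact (Clopper-Pearson) 95% limits; the SAP names no method, so that is an assumption.

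| Case, 4 CRs | Shown under SAP 4.2.2 | All treated |
|---|---|---|
| One patient replaced | 4/27 = 14.8% (4.2 to 33.7) | 4/28 = 14.3% (4.0 to 32.7) |
| Two patients replaced | 4/27 = 14.8% (4.2 to 33.7) | 4/29 = 13.8% (3.9 to 31.7) |
| One of 27 dropped, none replaced | 4/26 = 15.4% (4.4 to 34.9) | 4/27 = 14.8% (4.2 to 33.7) |

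The CR count is 4 in every cell, so the 4-CR verdict is the same.

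**3. Effect in a small dose level.** Take a phase Ib level of 3 patients, one replaced, with 2 responders. The report shows 2/3 = 67%; on all four treated patients it is 2/4 = 50%.

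**4. Effect of replacement on the error of the 4-CR rule.** This comes from replacement with a fixed cutoff, not from the exclusion sentence. Let q be the share of treated patients who progress before 8 weeks, and let them have no chance of a CR. If the all-treated CR rate is 0.05, the rate among the patients who remain is 0.05/(1 − q). Replacing until 27 remain gives an error of P(X ≥ 4 | 27, 0.05/(1 − q)). The chance of at least one such patient among 27 is 1 − (1 − q)^27.

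| q (assumed) | Rate among those who remain | Error | Chance of at least one in 27 |
|---|---|---|---|
| 0 | 0.0500 | 0.0437 | 0 |
| 1% | 0.0505 | 0.0451 | 24% |
| 2% | 0.0510 | 0.0465 | 42% |
| 5% | 0.0526 | 0.0512 | 75% |

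The error reaches 0.05 at about q = 4.3%.

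The documents do not give q. One rough guide is the 75% PFS at 26 months for ibrutinib alone in protocol 1.1.5.1. Under a constant hazard, −ln(0.75)/26 = 0.01106 per month. Eight weeks is 1.84 months, so q = 1 − exp(−0.01106 × 1.84) = 2.0%. That figure counts deaths and comes from refractory patients, so it may be high for this trial, which also enrols untreated patients.

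**The case against.** **The SAP is following the protocol.** Replacement of early progressors is pre-specified, and in protocol 10.5 it comes directly after the sentence on reaching 27 evaluable patients. One can read this as meaning that a replaced patient does not fill one of the 27 places; SAP 4.2.2 then applies that reading openly and in advance. This stands in part: the root is an ambiguity inside protocol 10.5. It does not settle the matter. The phrase about 27 evaluable patients is attached to patients who were never dosed, replacement governs enrolment, and 10.1 and 10.5 both point to all treated patients as the analysis set.

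**The effect is small and partly visible.** This stands. One replaced patient moves the primary rate by about half a percentage point, against an interval about 29 points wide. Reasons for discontinuation are tabulated (SAP 5.1) and PFS keeps these patients, so a reader could rebuild the all-treated rate. The dose-level rates in phase Ib are descriptive.

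**Some exclusions can be defended.** A phase Ib patient who progresses before ibrutinib starts at week 4 never received the combination. That supports keeping the present set as a sensitivity analysis, not as the only analysis.

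**A stronger reading that fails.** A reader might infer that the plan breaches its alpha. The documents do not support this. The stated level is 0.05, and 0.0437 is only what the exact calculation gives. At the one value of q that can be roughly tied to the documents, 2%, the error is 0.0465. It passes 0.05 only above about 4.3%. If the null CR rate is taken to refer to patients who remain after replacement, the error stays at 0.0437.

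**Conclusion.** The concern holds as a conflict over the denominator. SAP 4.2.2 removes treated failures from the primary and secondary response rates, while the protocol describes all dosed patients as evaluable for efficacy and leaves the status of replaced patients open. The direction of the effect is certain: the rates can only rise or stay the same. This rests on early progressors being unable to be in remission at week 52, which follows from their withdrawal under protocol 3.5.1.

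For the primary rate with 4 CRs, the size is 14.8% instead of 14.3% or 13.8% for one or two replaced patients. It is nil if there is no early progressor. For a dose level of 3 with one patient replaced it can be 67% instead of 50%.

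A reader might also infer that the exclusion could turn a negative trial positive. It cannot, because it leaves the number of CRs unchanged. Replacement raises the all-treated error only modestly, from 0.0437 to 0.0465 if 2% progress early, and beyond 0.05 only for a share that the documents do not give.

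**What to change.** 1. Delete the exclusion sentence in SAP 4.2.2.
2. Compute the CR, overall, PR and undetectable-MRD rates on all patients with at least one dose who meet the 52-week criterion, with early progressors counted as non-responders.
3. Keep the population as now defined in 4.2.2 as a sensitivity analysis.
4. Reconcile protocol 10.5 with the SAP by stating that a replaced patient who was dosed stays in the efficacy denominator.

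The cost is a few sentences and one extra table, and the reported rates may be slightly lower.

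The 4-CR rule can stay as it is. Tying it to the first 27 dosed patients is not proposed. That would cancel the replacement policy for the decision. It would also keep power at 0.818 only if 20% is the all-treated CR rate. If 20% applies to patients who do not progress early, the power is P(X ≥ 4 | 27, 0.20 × (1 − q)): 0.804 at q = 2% and 0.782 at q = 5%.

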4.3 Subgroup Definitions

No subgroup is defined.

4.4 Calculated Variables

- Baseline is defined as the last non-missing value done before the first dose
 of any study treatment, i.e. date ≤ first dose. Assessments done on the date
 of study treatment administration are assumed to take place before the
 administration, unless specified otherwise.
- **Treatment-emergent** (TE) data are defined as values after the first dose of any study treatment, i.e. date ≥ first dose, and before or on 28 days after the last dose of any study treatment, i.e. date ≤ last dose +28 days

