### Follow-up period:

Treatment by IPH2201 will be limited to 56 weeks, or less, in the event that a complete response with undetectable MRD is documented for 2 months.

[figure not shown]
Treatment by ibrutinib will be at least administered until the end of the study follow-up period (up to 12 months after end of IPH2201 treatment), unless disease progression (International Workshop on Chronic Lymphocytic Leukemia (IWCLL)), untoward toxicity, or consent withdrawal leads to the premature interruption of the ibrutinib treatment.

Patients will be enrolled for a post study follow-up enabling the investigator to document disease progression (IWCLL) or death, for 3 additional years after the completion of their in study follow-up.

Release date: 12 August 2016
Edition number

GED version MOD-3783

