### 3.4 DURATION OF STUDY

The recruitment of up to 45 patients is expected to approximately cover an 18-month period.

Patients in part 1 may be treated up to 56 weeks: 4 cycles of 2 weeks each followed by 12 cycles of 4 weeks each.

Patients in part 2 may be treated up to 52 weeks: 4 cycles of 2 weeks each followed by 11 cycles of 4 weeks each.

Treatment by ibrutinib will be at least administered until the end of the study follow-up unless a disease progression (IWCLL), untoward toxicity or consent withdrawal leads to the premature interruption of the treatment.

Patients will be followed for 12 months after interruption of IPH2201 treatment (End of Study visit). Furthermore, patients will be enrolled in a post study follow-up enabling the documentation of disease progression (IWCLL) or death for 3 additional years after the completion of their study follow-up.

CONFIDENTIAL

Release date: Edition number

GED version

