3.1 Study Objectives

3.1.1 Phase Ib

3.1.1.1 Primary Objective

The primary objective of the phase Ib is to assess the safety of monalizumab (IPH2201) given IV as a single agent and in combination with ibrutinib in patients with relapsed, refractory or previously untreated chronic lymphocytic leukemia. The two primary endpoints of the phase Ib are:

- Occurrence of DLT and identification, if any, of the MTD, during the administration of IPH2201 as a single agent and given in combination with ibrutinib
- Occurrence of AEs and SAEs

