3.2.1 Phase Ib

Monalizumab is administered as an intravenous infusion as a single agent during the first 2 administrations, at week 0 and week 2; ibrutinib is introduced as a combination therapy at week 4. Monalizumab is administered at week 4 and 6 and then every 4 weeks. Ibrutinib is administered orally once daily.

During the phase Ib, a 3+3 design will be employed. Four doses are planned to be assessed if MTD is not previously reached:

Dose level 1: 1 mg/kg

Dose level 2: 2 mg/kg

Dose level 3: 4 mg/kg

Dose level 4: 10 mg/kg

Three patients will be entered at each dose level. If a Dose Limiting Toxicity (DLT) is encountered in the initial cohort at a given dose level, that cohort will be expanded to a total of 6 patients. MTD will be considered to have been exceeded if >1/6 patients experience a DLT at that same dose level. MTD will be sought at the previous dose level by enrolling 3 additional patients, unless this cohort has been previously expanded to 6. If less than 2 out of 6 patients develop a DLT at that level, it will be defined as the MTD.

Dose-escalation will be based on a review by the safety committee of the data from all patients of the current cohort, after they have completed first 2 cycles of single agent monalizumab. Introduction of ibrutinib at a new dose level will be allowed by the safety committee after review of the data of all patients of the previous cohort, after they have completed 2 cycles of monalizumab in combination with ibrutinib.

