9.1 Dose Limiting Toxicity

For the patients enrolled in the phase Ib trial, the occurrence of dose limiting toxicity (DLT) and the type of DLT will be tabulated by dose level, and overall.

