9.3 Adverse Events

Adverse events (AEs) will be coded using the Medical Dictionary for Regulatory Activities and will be graded according to the National Center Institute Common Terminology Criteria for AEs (NCI-CTCAE criteria [v4.0] [3]). Adverse events will be analyzed in terms of their type, incidence, severity and relationship to the study treatment. Related AEs are defined as events with a relationship to study treatment equal to 'possibly related', 'probably related', or 'definitively related' or with missing relationship.

Adverse events in this section will be tabulated if they are treatment-emergent (TE), see definition in Section 4.4. Partial dates will be handled according Section 4.5.

A summary table will present the frequency of patients with at least one:

- TEAE
- TEAE related to monalizumab or ibrutinib
- TEAE related to monalizumab
- TEAE related to ibrutinib
- TEAE causing monalizumab or ibrutinib discontinuation
- TEAE causing monalizumab discontinuation
- TEAE causing ibrutinib discontinuation
- TEAE causing dose delayed of monalizumab
- TEAE causing monalizumab infusion interrupted
- TEAE causing dose reduction of monalizumab at the lower dose level
- TEAE causing dose reduction of ibrutinib
- TEAE causing dose interruption of ibrutinib
- Grade 3 or worse TEAE
- Serious TEAE
- Monalizumab or ibrutinib related serious TEAE
- Monalizumab related serious TEAE
- Ibrutinib related serious TEAE
- Fatal TEAE
- Fatal TEAE related to monalizumab or ibrutinib

In addition, tabulations of the number of patients who experienced TEAEs as well as severity of the events will be presented by SOC and PT, by grade, by dose and overall. Patients will only be counted once for each preferred term. In case a patient experienced the same event more than once, the worst severity will be presented.

The following tabulations will be presented:

TPL Version: 02

[figure not shown]
- All TEAEs
- Monalizumab or ibrutinib related TEAEs
- Monalizumab related TEAEs
- Ibrutinib related TEAEs
- TEAE causing monalizumab or ibrutinib discontinuation
- TEAE causing monalizumab discontinuation
- TEAE causing ibrutinib discontinuation
- TEAE causing dose reduction of monalizumab at the lower dose level
- TEAE causing dose reduction of ibrutinib
- Grade 3 or worse TEAE
- Serious TEAEs
- Monalizumab or ibrutinib related Serious TEAEs
- Monalizumab related Serious TEAEs
- Ibrutinib related Serious TEAEs
- Fatal TEAE

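### SAP 9.1 and 9.3 plan no DLT or adverse-event table by treatment period, although the phase Ib primary objective names IPH2201 safety both alone and with ibrutinib

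*SAP*

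**What the plan says.** **Objective and endpoint.** SAP 3.1.1.1 sets the phase Ib primary objective as the safety of monalizumab (IPH2201) "given IV as a single agent and in combination with ibrutinib". One primary endpoint is "Occurrence of DLT and identification, if any, of the MTD, during the administration of IPH2201 as a single agent and given in combination with ibrutinib"; the other is the occurrence of AEs and SAEs.

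**Schedule.** SAP 3.2.1 describes how IPH2201 dosing begins: "as a single agent during the first 2 administrations, at week 0 and week 2; ibrutinib is introduced as a combination therapy at week 4". Protocol 3.4 gives the length: "Patients in part 1 may be treated up to 56 weeks: 4 cycles of 2 weeks each followed by 12 cycles of 4 weeks each". The protocol synopsis (Follow-up period) adds: "Treatment by ibrutinib will be at least administered until the end of the study follow-up period". That period lasts up to 12 months after IPH2201 ends, unless progression, toxicity or withdrawal of consent intervenes.

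**Adverse-event window.** SAP 4.4 uses one treatment-emergent window for both drugs. It opens at the first dose of either and covers events after that "and before or on 28 days after the last dose of any study treatment".

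**Tables.** SAP 9.3 has treatment-emergent AEs "presented by SOC and PT, by grade, by dose and overall". Each patient counts once per preferred term, at the worst severity. There are further versions by relatedness to each drug. Under SAP 9.1 the occurrence and type of DLT "will be tabulated by dose level, and overall". SAP 4.3 defines no subgroup.

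**The concern.** The primary objective has two parts, and the trial is run in two parts. Protocol 9.3 has the safety committee look at each dose level first after the single-agent cycles and again after two combination cycles. The final tables drop that distinction. A reader of the study report who wants the incidence of, say, infection or cytopenia on IPH2201 alone, or on the combination, would find neither. Both are merged with events from the follow-up year on ibrutinib.

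The counting rule adds to this. With one count per term at worst grade, a milder event on IPH2201 alone is overwritten if the same term returns at a higher grade later.

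The relatedness tables do not replace a split by period. They rest on investigator attribution in an open-label two-drug regimen, whereas onset relative to the first ibrutinib dose is a matter of dates.

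**Working it through.** **1. The plan's own schedule.** Phase Ib (Protocol 3.4): 4 × 2 + 12 × 4 = 8 + 48 = 56 weeks, as stated. The single-agent part is two 2-week cycles, or 4 weeks. That leaves 56 − 4 = 52 weeks of combination, which agrees with Protocol 3.2. The last scheduled dose at week 52 plus 28 days falls at week 56.

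**2. Nominal content of the AE window, phase Ib.** Inputs: 4 weeks alone, 52 weeks combined, *c* weeks on ibrutinib after IPH2201, and the 4-week (28-day) tail of SAP 4.4. The window is 4 + 52 + *c* + 4. The documents give no completion rate, so *c* is an assumption, varied from 0 to 52 (12 months taken as 52 weeks).

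| *c* (weeks) | Window (weeks) | IPH2201 alone | Combination | Ibrutinib after IPH2201 | Tail |
|---|---|---|---|---|---|
| 0 | 60 | 6.7% | 86.7% | 0% | 6.7% |
| 26 | 86 | 4.7% | 60.5% | 30.2% | 4.7% |
| 52 | 112 | 3.6% | 46.4% | 46.4% | 3.6% |

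Without the tail, *c* = 52 gives 4/108 = 3.7%, 52/108 = 48.1% and 48.1%. The figure of 108 weeks is close to what will be observed. Protocol 9.1.2 collects AEs routinely to the end-of-study visit, and the protocol's visit correlation table puts that visit one week after month 12.

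**3. Phase IIa.** Treatment lasts 4 × 2 + 11 × 4 = 52 weeks. A nominal 52-week follow-up on ibrutinib is then 52/104 = 50% of calendar time. SAP 4.1 also puts the phase Ib patients treated at the recommended dose into all outputs of both phases. That is 3/27 = 11% to 6/27 = 22% of the 27 patients, so the phase IIa tables also contain some single-agent weeks.

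**4. DLTs.** Protocol 9.3 defines the DLT window as the first four cycles, 8 weeks: 4 alone and 4 combined, or 50% each, with no scheduled time on ibrutinib alone. The treatment-emergent filter is stated in SAP 9.3 for that section only. SAP 4.4 therefore does not set the DLT window. The missing split comes from SAP 9.1 itself.

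**5. Counting rule.** Suppose a patient has a grade 1 event in week 1 and the same preferred term at grade 3 during follow-up. The table shows one patient at grade 3, and nothing shows that the event first appeared before ibrutinib.

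**6. Partial dates.** SAP 4.5 moves an AE start date with a missing day to the end of the month, capped at the last study treatment. If the same temporary date were used to assign a period, every single-agent event with a missing day in the calendar month in which ibrutinib starts would land in the combination period.

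**The case against.** The case for leaving the SAP alone is substantial.

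- Protocol 10.1 makes the analyses descriptive. No test, escalation rule or go/no-go criterion depends on the layout of these tables. Dose decisions rest on the safety committee's reviews, which do separate the two parts.
- SAP 4.1 plans individual listings for all tabulated data, and the SAE listing in SAP 9.3 carries onset dates. With 3 to 6 patients per dose level and ibrutinib scheduled to start at week 4, a split can be rebuilt.
- The long window matches AE collection to the end of study and does not lose late IPH2201 effects.

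These points stand, and they lower the severity. They do not supply a prespecified summary of a primary endpoint: rebuilding it from listings is done after the event and by rules nobody has fixed.

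Some stronger readings are tempting, but the documents do not support them:

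- *The pooled window is why the DLT table is unsplit.* It is not; see step 4.
- *The primary question cannot be answered.* It can, from the data collected; the planned tables do not do it.
- *About half of the combination events are really ibrutinib-only events.* No table is labelled as combination, and the shares are time, not events. Visit intensity differs sharply: the phase I flow chart has 10 visits from week 0 to week 6, against 8 (FU1 to FU7 and end of study) over the follow-up year.
- *Time beyond 28 days after the last IPH2201 dose is free of IPH2201.* The SAP's phase I flow chart samples pharmacokinetics and receptor saturation through follow-up, Protocol 4.1 requires contraception for 5 months after the last dose, and no half-life is given.
- *Period columns isolate the effect of each drug.* The periods are not randomised and are confounded with time on study.

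**Conclusion.** The concern holds as a reporting gap. Followed as written, SAP 9.1 and 9.3 yield no table that reports either part of the phase Ib primary objective separately. For AEs the cause is the single window together with tables that have no period column, and worst-grade counting can hide a single-agent event. For DLTs the cause is only that SAP 9.1 does not divide its 8 weeks.

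The size is stated in calendar time. Single-agent weeks are about 4% of a phase Ib completer's window, and 6.7% if ibrutinib stops at week 56. The share on ibrutinib after IPH2201 runs from 0% to 48% depending on how long it continues. This rests on the nominal schedule, with 12 months taken as 52 weeks. No event share or bias can be derived from the documents.

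Sample size, alpha and power are unaffected. Severity: should fix. SAP 9.5 is not in the available text and is not counted against the plan.

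**What to change.** Keep the overall treatment-emergent tables, and add to SAP 4.4, 9.1 and 9.3:

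1. **AE columns by onset date.** (a) IPH2201 alone, before the first ibrutinib dose: phase Ib patients, including those carried into the phase IIa outputs. (b) Combination, from the point when both drugs have started to the last IPH2201 dose + 28 days. (c) Later than that, labelled post-IPH2201 and not described as free of IPH2201 exposure.
2. **Counting.** Apply worst-grade counting within each period and give patient-time per period. Protocol 9.1.2.1 already requires a new record when an event worsens, so a worsening has its own onset date.
3. **DLTs.** Split by onset before, versus on or after, the first ibrutinib dose (nominally weeks 0–4 and 4–8).
4. **Partial dates.** State how an AE with an incomplete start date is assigned to a period, rather than letting the month-end rule of SAP 4.5 decide it.
5. **Ibrutinib stopped first.** State how patients who stop ibrutinib but continue IPH2201 are classified, since Protocol 3.3.2 allows this.
6. **Reporting.** Report combination safety from column (b) alongside the overall table, not instead of it.

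The cost is SAP wording and a little programming. Onset dates are recorded under Protocol 9.1.2, and SAP 9.2 already uses dosing dates for both drugs. The drawback is small numbers per column, which suits description only.
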